### **7.5.10 Treatment-free interval**

Treatment free interval and survival will be summarized in months (median and 95% CI) and rates will be provided at 1, 2, 3, 6, 9, 12, 24, 36, 48, and 60 month intervals. Kaplan-Meier plot of treatment-free interval and survival will be provided.

## **7.6 Safety**

### **7.6.1 Deaths**

Deaths will be summarized by treatment group:

- All deaths, reasons for death

- Deaths within 30 days of last dose received, reasons for death
- Deaths within 100 days of last dose received, reasons for death

By-subject listing of deaths will be provided for the all enrolled subjects population.

### **7.6.2 Serious Adverse Events**

Serious adverse events will be summarized by treatment group:

- Overall summary of SAEs by worst CTC grade (any grade, grade 3-4, grade 5) presented by SOC/PT
- Overall summary of drug-related SAEs by worst CTC grade (any grade, grade 3-4, grade 5) presented by SOC/PT.

All analyses will be conducted using the 30-day safety window.

By-subject SAE listing will be provided for the “enrolled subjects” population.

### **7.6.3 Adverse Events Leading to Discontinuation of Study Therapy**

AEs leading to discontinuation will be summarized by treatment group:

- Overall summary of AEs leading to discontinuation by worst CTC grade (any grade, grade 3-4, grade 5) presented by SOC/PT.
- Overall summary of drug-related AEs leading to discontinuation by worst CTC grade (any grade, grade 3-4, grade 5) presented by SOC/PT.

The analyses will be conducted using the 30-day safety window. By-subject AEs leading to discontinuation listing will be provided.

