Procedure	Follow-Up ^a Visits 1 and 2	Survival Follow- Up Visits ^b	Notes
Exploratory Biomarker Testing			
Tumor Tissue Biopsy and Biomarker Assessments			See Table 9.8.2.6-1 .

^a Follow-up visits occur as follows: Follow-up Visit 1 = 30 days from the last dose (± 7 days) or coincide with the date of discontinuation (± 7 days) if date of discontinuation is greater than 42 days after last dose. Follow-up Visit 2 = 100 days (± 7 days) from last dose of study treatment. Participants must be followed for at least 100 days after last dose of study treatment. Both follow-up visits should be conducted in person.

^b Survival follow up visits may be conducted in clinic or by phone. Survival visits: first Survival Follow-up visit 3 months (± 14 Days) after FU 2, subsequent survival FU visits every 3 months (± 14 days). BMS may request that survival data be collected on all treated participants outside of the 3 month specified window. At the time of this request, each participant will be contacted to determine their survival status unless the participant has withdrawn consent for all contacts.

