7.1.1 BMS-986213 or Nivolumab Dosing

BMS-986213 (prepared in normal saline for relatlimab 160 mg/nivolumab 480 mg) or nivolumab 480 mg dosing is to be administered as an IV infusion through a 0.2-micron to 1.2-micron pore-size, low-protein binding in-line filter at the protocol-specified doses. It is not to be administered as an IV push or bolus injection. Instructions for dilution and infusion of relatlimab/nivolumab or nivolumab injection will be provided in the pharmacy binder. Care must be taken to assure sterility of the prepared solution as the product does not contain any antimicrobial preservative or bacteriostatic agent.

Participants should receive BMS-986213 or nivolumab as a 1-hour infusion on Day 1 of each treatment cycle until progression, unacceptable toxicity, withdrawal of consent, or the study ends,

whichever occurs first. Participants should begin study treatment within 3 calendar days of randomization.

The sponsor, participants, investigator, and site staff will be blinded to the study drug administered. Each investigative site must assign an unblinded pharmacist/designee.

There will be no dose escalations or reductions of any study treatment allowed. Participants may be dosed within a ± 3 day window (ie, participants may be dosed no less than 25 days and no more than 31 days between doses). Premedication is not recommended for the first dose of either treatment.

Participants should be carefully monitored for infusion reactions during administration. If an acute infusion reaction is noted, participants should be managed according to [Section 7.7.3](#).

Doses may be interrupted, delayed, or discontinued depending on how well the participant tolerates the treatment. Dosing visits must not be skipped, only delayed.

Infusions are compatible with polyvinyl chloride (PVC) or polyolefin containers and infusion sets, and glass bottles.

Care must be taken to assure sterility of the prepared solution as the product does not contain any antimicrobial preservative or bacteriostatic agent.

For details on prepared drug storage, preparation, and administration, please refer to the IBs and/or pharmacy binder.

The selection and timing of dose for each participant is provided in [Table 7.1-1](#).

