8.1.1 Dose Discontinuation

If a participant in any of the nivolumab/relatlimab combination arms meets criteria for discontinuation in [Table 7.4-1](#), the participant must discontinue both nivolumab and relatlimab and be taken off the treatment phase of the study.

Nivolumab and relatlimab treatment must be permanently discontinued per criteria in [Table 7.4-1](#) in [Section 7.4](#) (Dosage Modification). Discontinue from study treatment for any AE, laboratory abnormality, or intercurrent illness that, in the judgment of the investigator, presents a substantial clinical risk to the participant with continued nivolumab or relatlimab dosing.

Study treatment must also be permanently discontinued for the following:

- Any event that leads to delay in dosing lasting > 8 weeks from the previous dose requires discontinuation, with the following exceptions:
- Dosing delays to allow for prolonged steroid tapers to manage drug-related AEs are allowed.
- Dosing delays lasting > 8 weeks from the previous dose that occur for non-drug-related reasons may be allowed if approved by the BMS Medical Monitor (or Clinical Scientist).
- Tumor assessments should continue as per protocol even if dosing is delayed. Periodic study visits to assess safety and laboratory studies should also continue every 6 weeks or more frequently if clinically indicated during such dosing delays.

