## 6 STUDY PERIODS, TREATMENT REGIMENS AND POPULATIONS FOR ANALYSES

### 6.1 Study Periods

Each treated subject will go through two study periods: baseline period and post baseline period.

- Baseline period:
    - Baseline evaluations or events will be defined as evaluations or events that occur before the date and time of the first dose of study treatment. Evaluations on the same date and time of the first dose of study treatment will be considered as baseline evaluations.
    - In cases where the time (onset time of event or evaluation time and dosing time) is missing or not collected, the following definitions will apply:
      - ◆ Pre-treatment AEs will be defined as AEs with an onset date prior to but not including the day of the first dose of study treatment
      - ◆ Baseline evaluations (laboratory tests, pulse oximetry and vital signs) will be defined as evaluations with a date on or prior to the day of first dose of study treatment
- If there are multiple valid assessments, the assessment that is closest to day (and time if collected) of the first dose of study treatment will be used as the baseline in the analyses. If multiple assessments are collected on the same date (and time, if collected), the last assessment will be considered as baseline.

- Post baseline period:
  - On-treatment AEs will be defined as AEs with an onset date and time on or after the date and time of the first dose of study treatment (or with an onset date on or after the day of first dose of study treatment if time is not collected or is missing). For subjects who are off study treatment, AEs will be included if event occurred within a safety window of 30 days (or 100 days depending on the analysis) after the last dose of study treatment. No “subtracting rule” will be applied when an AE occurs both pre-treatment and post-treatment with the same preferred term and grade.
  - On-treatment evaluations (laboratory tests, pulse oximetry and vital signs) will be defined as evaluations taken after the day (and time, if collected and not missing) of first dose of study treatment. For subjects who are off study treatment, evaluations should be within a safety window of 30 days (or 100 days depending on the analysis) after the last dose of study treatment.
  - If more than one tumor biopsy specimen is available, baseline PD-L1 and LAG-3 expression will be determined from the most recently collected specimen (prior to first dose of study treatment) with a measurable result

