### **7.6.14 Hematology**

The following will be summarized by treatment group as worst CTC grade on-treatment per subject and as shift table of worst on-treatment CTC grade compared to baseline CTC grade per subject: hemoglobin (HB), platelets, white blood counts (WBC), absolute neutrophils count (ANC) and lymphocyte count (LYMPH).

The analyses will be conducted using the 30-day safety window.

A by-subject listing of these laboratory parameters will be provided.

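### The overall SAE, discontinuation-AE and laboratory tables stop 30 days after last dose, but a dose hold may run to 8 weeks or longer before treatment ends, so late-onset events in participants never redosed are left out

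*SAP*

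**What the plan says.** **The window.** SAP 6.1 sets the rule for participants who have stopped dosing: "AEs will be included if event occurred within a safety window of 30 days (or 100 days depending on the analysis) after the last dose". It counts from the last dose, not from the date of the decision to discontinue. The same section applies the rule to laboratory evaluations by the date they were taken.

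**Where 30 days is the only window.**
- SAP 7.6.2, serious adverse events: "All analyses will be conducted using the 30-day safety window".
- SAP 7.6.3, AEs leading to discontinuation: "The analyses will be conducted using the 30-day safety window. By-subject AEs leading to discontinuation listing will be provided".
- SAP 7.6.14, hematology: "The analyses will be conducted using the 30-day safety window". Sections 7.6.15 to 7.6.17 (chemistry, electrolytes, hepatic and thyroid abnormalities) say the same.

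**How long a participant can go between doses.** On schedule, Protocol 7.1.1 says that "participants may be dosed no less than 25 days and no more than 31 days between doses". Protocol 8.1.1 requires discontinuation once a delay passes 8 weeks from the previous dose, with exceptions. One is that "Dosing delays to allow for prolonged steroid tapers to manage drug-related AEs are allowed", with no upper limit. Another covers approved delays for reasons unrelated to the drug.

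**Follow-Up Visit 1.** Protocol Table 2-3 requires hematology and chemistry at this visit. It falls 30 days (± 7) after the last dose, or is set to "coincide with the date of discontinuation (± 7 days) if date of discontinuation is greater than 42 days after last dose".

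**Collection.** Protocol Table 2-3 and Section 9.2.1 have AEs and SAEs collected for 100 days after treatment. For SAEs there is a limit once a new anti-neoplastic therapy has started.

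**The concern.** Everyone in the discontinuation table has, by definition, received a last dose and not been redosed. For these participants the 30-day clock starts at that dose, while the protocol allows the hold before the final decision to last much longer. A new event arising late in the hold can be the reason treatment ends, and be recorded as such under SAP 7.1.1, yet be absent from the table meant to count it. The same event in a participant who is later redosed is counted, because the last dose has moved past it. Inclusion thus depends on whether dosing resumed, which is the outcome the table reports.

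Laboratory values raise a related problem, because the rule tests the date of the sample. An AE that starts on day 25 stays in the AE tables, but a peak transaminase or bilirubin measured after day 30 in a participant never redosed does not reach the worst-grade or hepatic tables. Protocol 7.4.3 calls for laboratory studies to continue during holds, so such samples are expected.

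SAEs, AEs leading to discontinuation and laboratory abnormalities are named safety endpoints in Protocol Table 4-1. At stake is whether their headline rates by arm are complete.

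**Working it through.** Days are counted from the last dose received. This is day arithmetic; no power or sample-size formula applies.

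**1. The protocol's own figure.** The cycle is 4 weeks = 28 days and the dosing window is ± 3 days. 28 − 3 = 25 and 28 + 3 = 31, which reproduces the stated 25 to 31 days. Against a 30-day window the nominal 28-day interval is covered, and the longest on-schedule interval exceeds it by 31 − 30 = 1 day.

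**2. Dose holds.** The 8-week limit is 8 × 7 = 56 days. Uncovered days = max(0, gap − window).

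| Last dose to discontinuation (days) | Uncovered, 30-day window | Share of gap | Uncovered, 100-day window |
|---|---|---|---|
| 28 | 0 | 0% | 0 |
| 31 | 1 | 3% | 0 |
| 42 | 12 | 29% | 0 |
| 56 | 26 | 46% | 0 |
| 70 | 40 | 57% | 0 |
| 84 | 54 | 64% | 0 |

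The last two rows are possible only under the exceptions in Protocol 8.1.1. The shares are shares of days, not of events.

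**3. Which events are lost.** SAP 6.1 tests when the event occurred. Three cases, each with the next dose held:
- AE starts on day 25, treatment ends on day 56. Since 25 ≤ 30, it is counted.
- New AE starts on day 42 and dosing later resumes. The last dose is then after the event, so it is counted.
- New AE starts on day 42 and the participant is never redosed. Since 42 > 30, it is excluded from 7.6.3 and, if serious, from 7.6.2.

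Only the third pattern is lost.

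**4. Follow-Up Visit 1 laboratory values.** The usual range is 30 − 7 = 23 to 30 + 7 = 37, which is 15 permitted days. Days 31 to 37 are outside the window: 7 of 15. Days 23 to 30, the other 8, are inside. If discontinuation is more than 42 days after last dose, its earliest date is day 43 and the earliest visit is 43 − 7 = day 36. All these visits are outside.

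**5. What is recovered elsewhere.**

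| SAP section | Window | What it leaves open |
|---|---|---|
| 7.6.1 Deaths | all, 30 and 100 days | deaths only |
| 7.6.5 AEs at ≥ 5% incidence; drug-related AEs | 30 and 100 days | does not identify serious or treatment-ending events |
| 7.6.7 Select AEs (EU), including serious and discontinuation | 30 days only | same gap |
| 7.6.10 Immune-mediated AEs (US), including serious and discontinuation | 100 days | those breakdowns require immune-modulating medication, except for endocrine events |
| 7.6.11 Other events of special interest | 100 days | no serious or discontinuation breakdown |

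**6. Size, by assumption only.** The documents give no onset distribution. If a fraction f of discontinuation AEs starts after day 30 in participants never redosed, the tabulated rate is true rate × (1 − f). With f assumed at 5% to 20%, a true 10% would appear as 9.5% to 8.0%. A true 15% of about 350 per arm (700 ÷ 2) is 52.5 participants and would appear as 49.9 to 42.0.

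**The case against.** The strongest reply is that the SAP uses 100 days where it matters most for this drug class. A late hepatitis during a hold, treated with immune-modulating medication and with no clear alternate cause, enters the 100-day immune-mediated table for events leading to discontinuation and, if serious, the serious one. If judged drug-related, it also enters the 100-day drug-related table. Myocarditis and troponin elevation fall under other events of special interest, also at 100 days. By-subject listings of SAEs, discontinuation AEs and laboratory values are planned, clinically significant laboratory results are reported as AEs, and a 30-day window aids comparison across studies.

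Much of this stands. A reader might infer that treatment-ending AEs drop out in general. They do not, because the rule tests onset rather than the date of discontinuation. A reader might also infer that ordinary on-schedule dosing defeats the window; that is a one-day edge case at day 31. Nor does late immune-mediated toxicity vanish from the tables.

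What remains is that none of these tables gives the overall SAE rate, discontinuation-AE rate or laboratory-abnormality rate beyond 30 days. The immune-mediated breakdowns are for the US submission and mostly conditional on medication; the EU counterpart stays at 30 days. Listings give no rates by arm.

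**Conclusion.** The gap is real but limited. AEs and SAEs with new onset more than 30 days after last dose, in participants never redosed, are left out of SAP 7.6.2 and 7.6.3, and laboratory values drawn after day 30 in such participants are left out of 7.6.14 to 7.6.17. In days, that is up to 26 of 56 in an 8-week hold, more under the exceptions, 7 of 15 for the usual Follow-Up Visit 1, and all of the later-scheduled ones. This rests on reading SAP 6.1 as written, with the window running from the last dose for anyone off treatment at the time of analysis.

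The number of events affected is unknown, and the percentages in step 6 are illustrations. A reader might infer that the rule hides excess toxicity in the combination arm. The documents do not support that: they give no hold, onset or discontinuation pattern by arm, and longer or more frequent holds lose nothing when dosing resumes. The rates in these tables may be too low; neither the size nor the direction of any between-arm effect can be derived. The tables should be supplemented, at low cost, but the safety analysis as a whole is not undermined.

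**What to change.** - In SAP 7.6.2 and 7.6.3, repeat the SAE and discontinuation-AE tables, all and drug-related, with the 100-day window.
- In SAP 7.6.14 to 7.6.17, repeat the summaries with the 100-day window, or include laboratory values from dose holds and Follow-Up Visit 1 whenever they were drawn.
- Keep the 30-day tables for comparison across studies.

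A 100-day window leaves no uncovered day for any hold in the working table and covers Follow-Up Visit 1 on days 23 to 37.

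The cost is SAP wording and a few repeat tables on data already being collected, with no change to conduct or efficacy analysis. Reported rates would rise slightly. Two limits should be footnoted. SAE collection narrows once a new anti-neoplastic therapy starts (Protocol 9.2.1), and Follow-Up Visit 2 laboratory tests are repeated only if treatment-related toxicity persists (Protocol Table 2-3).

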### **7.6.4 Adverse Events Leading to Dose Modification**

AEs leading to dose delay/reduction will be summarized by treatment group:

- Overall summary of AEs leading to dose delay/reduction by worst CTC grade (1, 2, 3, 4, 5, not reported, total) presented by SOC/PT

The analysis will be conducted using the 30-day safety window.

By-subject AEs leading to dose delay/reduction listing will be provided.

### **7.6.5 Adverse Events**

Adverse events will be summarized by treatment group.

The following analyses will be conducted using the 30 days safety window only:

- Overall summary of any AEs by worst CTC grade (1, 2, 3, 4, 5, not reported, total) presented by SOC/PT

- Overall summary of any non-serious AEs presented by SOC/PT. This table will be restricted to events with an incidence greater or equal to 5% in any treatment group
- Overall summary of any AEs that required immune modulating medication by worst CTC grade (any grade, grade 3-4, grade 5) presented by SOC/PT.

The following analyses will be conducted using the 30 days safety window and repeated using the 100 days safety window:

- Overall summary of any AEs by worst CTC grade (any grade, grade 3-4, grade 5) presented by SOC/PT. This table will be restricted to events with an incidence greater or equal to 5% in any treatment group.
- Overall summary of drug-related AEs by worst CTC grade (any grade, grade 3-4, grade 5) presented by SOC/PT.

By-subject AE listing will be provided. By-subject listing of any AE requiring immune modulating medications will also be provided.

#### **7.6.6 Select Adverse Events (EU Submission)**

Unless otherwise specified, analyses will be performed by select AE category. Some analyses may also be repeated by subcategory of endocrine events.

#### **7.6.7 Incidence of Select AE**

Select AEs will be summarized by treatment group for each category/subcategory.

The following analyses will be conducted using the 30-day safety window only:

- Overall summaries of any select AEs by worst CTC grade (any grade, grade 3-4, grade 5) presented by Category or Subcategory/PT
- Overall summaries of any drug-related select AEs by worst CTC grade (any grade, grade 3-4, grade 5) presented by Category or Subcategory/PT
- Overall summary of any serious select AEs by worst CTC grade (any grade, grade 3-4, grade 5) presented by Category or Subcategory /PT
- Overall summary of drug-related serious select AEs by worst CTC grade (any grade, grade 3-4, grade 5) presented by Category or Subcategory /PT
- Overall summary of any select AEs leading to discontinuation by worst CTC grade (any grade, grade 3-4, grade 5) presented by Category or Subcategory /PT
- Overall summaries of drug-related select AEs leading to discontinuation by worst CTC grade (any grade, grade 3-4, grade 5) presented by Category or Subcategory /PT
- Summary of frequency of unique select AEs By-subject select AE listing will be provided.

### **7.6.8 Time-to Onset of Select AE**

Time to onset of drug-related select AEs (any grade, grade 3-5) will be summarized for each category/subcategory by treatment group.

Time-to onset analyses are restricted to treated subjects who experienced at least one drug-related select AE in the category/subcategory. The analyses will be conducted using the 30-day safety window.

Additional details regarding the time-to onset definition are described in time-to onset definition subsection of [Appendix 1](#).

### **7.6.9 Time-to Resolution of Select AE**

Time to resolution of the following specific events will be summarized separately for each category/subcategory.

- Time-to resolution of drug-related select AE (any grade, grade 3-5) by treatment group
- Time-to resolution of drug-related select AE (any grade, grade 3-5) where immune modulating medication was initiated, by treatment group

Time-to resolution analyses are restricted to treated subjects who experienced the specific events. Time-to resolution where immune modulating medication was initiated analyses are restricted to treated subjects who experienced the specific events and who received immune modulating medication during the longest select AE.

The following summary statistics will be reported: percentage of subjects with resolution of the longest select AE, median time-to resolution along with 95% CI (derived from Kaplan-Meier estimation) and ranges.

See time-to resolution definition subsection of Appendix 1 for additional details. The analyses will be conducted using the 30-day safety window.

### **7.6.10 Immune-Mediated Adverse Events (US Submission)**

IMAEs will be summarized by treatment group for each immune mediated category / PT using the 100-day safety window:

- Overall summary of AEs by worst CTC grade (any grade, grade 3-4, grade 5) presented by immune mediate Category / PT. This summary includes all AEs that are qualified for IMAE preferred terms list, without requirement of either usage of immune modulating medications or accounting for immune mediated etiology or immune mediated component. Overall summaries of IMAEs by worst CTC grade (any grade, grade 3-4, grade 5) where immune modulating medication was initiated presented by Category / PT.
- Overall summaries of endocrine IMAEs by worst CTC grade (any grade, grade 3-4, grade 5) presented by Category / PT.
- Overall summaries of serious IMAEs by worst CTC grade (any grade, grade 3-4, grade 5) where immune modulating medication was initiated presented by Category / PT.

- Overall summaries of endocrine serious IMAEs by worst CTC grade (any grade, grade 3-4, grade 5) presented by Category / PT.
- Overall summaries of IMAEs leading to discontinuation by worst CTC grade (any grade, grade 3-4, grade 5) where immune modulating medication was initiated presented by Category / PT.
- Overall summaries of endocrine IMAEs leading to discontinuation by worst CTC grade (any grade, grade 3-4, grade 5) presented by Category / PT.
- Overall summaries of IMAEs leading to dose delay or reduction by worst CTC grade (any grade, grade 3-4, grade 5) where immune modulating medication was initiated presented by Category / PT
- Overall summaries of endocrine IMAEs leading to dose delay or reduction by worst CTC grade (any grade, grade 3-4, grade 5) presented by Category / PT.
- Summaries of time to onset and time to resolution of IMAEs where immune modulating medication was initiated presented by Category.
- Summaries of time to onset and time to resolution of endocrine IMAEs presented by Category.

By-subject listing of IMAEs will be provided. By-subject listings of time to resolution for longest IMAEs cluster (any grade and grade 3-5 in separate summaries) will also be provided. For new studies which collect investigator assessment of potential IMAE data, a listing of Adverse Events Considered as Immune-Mediated Events per Investigator but not Qualified for Immune-Mediated Adverse Events Definition will also be provided.

In addition, for all nivolumab treated subjects who experienced at least one immune-mediated adverse event, the following data presentation will be provided:

- Summary of subjects who were re-challenged with nivolumab by immune-mediated adverse event category, with extended follow-up
- Summary of subjects who were re-challenged with BMS986213 or nivolumab by immune-mediated adverse event category, with extended follow-up

For these, re-challenge is considered to have occurred when last BMS986213 or nivolumab infusion was administered after the onset of an IMAE.

